#### **4.3.3 Subsequent Therapy**

Since the trial population comprises healthy subjects only, no subsequent therapy is planned.

#### **4.4 Withdrawal Criteria**

Since this is a single injection trial no specific withdrawal criteria are defined. The subject will be withdrawn from the trial if any of the inclusion or exclusion criteria during the conduct of the trial is violated in a way that invalidate subsequent assessments. The sponsor, and the investigator in agreement with the sponsor, reserves the right to discontinue the trial at any time for safety reasons or other reasons jeopardising the justification of the trial. Such a termination will be implemented in a time frame that is compatible with the subject's well-being. If the trial is prematurely terminated or suspended, the investigator should promptly inform the subjects and assure appropriate follow-up and treatment if required. Ferring Pharmaceuticals will notify the regulatory authorities of any plans to terminate the trial, and the investigator will notify the independent ethics committee (IEC)/institutional review board (IRB).

The subjects have the right to withdraw from the trial at any time for any reason, without the need to justify their decision. For any discontinuation, the investigator will obtain all the required details and document the date of the premature termination and the main reason in the e-CRF.

#### **4.5 Subject Replacement**

Subjects that are withdrawn may be replaced to reach 8 completed subjects at each dose level.

## 5 TREATMENTS

### 5.1 Treatments Administered

#### Investigational Medicinal Product

The subjects will receive a single subcutaneous abdominal injection of FE 999049 (follitropin delta). The doses administered will be 12, 18, and 24 µg according to randomisation.

#### Non-investigational Medicinal Product

The subjects will receive two subcutaneous abdominal injections of a 1-month depot formulation of the GnRH agonist DECAPEPTYL Depot 3.75 mg (Triptorelin).

### 5.2 Medicinal Products

#### 5.2.1 Characteristics and Source of Supply

Ferring Pharmaceuticals will provide the clinical site conducting the trial with FE 999049 and DECAPEPTYL Depot 3.75 mg in amounts sufficient for the trial. FE 999049 will be provided as cartridges with an isotonic phosphate buffered solution of pH 6.5 containing 33.3 µg/mL rhFSH (72 µg in 2.16 mL) and an injection pen. DECAPEPTYL Depot 3.75 mg will be provided as powder and solvent for suspension for injection.

#### 5.2.2 Packaging and Labelling

Packaging and labelling of the IMP and non-investigational medicinal product (NIMP) will be carried out under the responsibility of the Clinical Trial Supply (CTS) Department, Ferring Pharmaceuticals, Copenhagen, Denmark. The IMP and NIMP will be packed and labelled according to Good Manufacturing Practice (GMP), as well as any national regulatory requirements. All medicinal products will be labelled with trial specific labels, which contain a self-adhesive tear off portion to be affixed to the subject dispensing log maintained at trial site.

#### 5.2.3 Conditions for Storage and Use

The trial medication delegate will ensure that the medicinal products will be stored in appropriate conditions in a secure location with controlled access. The storage compartment shall be monitored regularly and the temperature shall be documented. Deviations in storage temperature must be reported to Ferring as instructed in the IMP/NIMP manual.

In case of technical malfunction of an administration pen, all relevant details (including time, date, a description of the malfunction and whether dosing was affected) of the incidence should be reported in the e-CRF, the pen should be replaced and the treatment continued. Human errors such as misunderstanding of instructions or incorrect handling of the device should not be regarded as technical malfunctions. In case of adverse events caused by malfunction of the administration pen, these will be identified and described.

### 5.3 Blinding/Unblinding

This is an open-label trial.

#### **5.4 Treatment Compliance, Dispensing and Accountability**

The IMP will only be dispensed to subjects who meet the eligibility criteria and are randomised to a treatment group in the trial.

The investigator (or his/her designated staff, e.g. trial nurse) will maintain a drug-dispensing log detailing the dates and quantities of IMPs/NIMPs dispensed to, and used by, each subject, as well as the batch numbers, IMP/NIMP numbers (or other identifier used in the trial).

The monitor will verify the drug accountability during the trial and if applicable document any discrepancies.

The IMP and NIMP will be administered by authorised staff at the clinical investigation unit. Compliance is assessed by recording the amount administered.

#### **5.5 Return and Destruction of Medicinal Products and Auxiliary Supplies**

All dispensed IMP and NIMP is to be destroyed at the trial site in accordance with local legislation after the drug accountability has been finalised and verified by the monitor.

Any non-dispensed IMP and NIMP must be returned for destruction, as instructed by the Ferring CTS Department, after the drug accountability has been finalised and verified by the monitor.

## 6 TRIAL PROCEDURES

The trial comprises 14 visits, 1 of which is the residential treatment visit. The duration of the trial including the screening period and the follow-up visits will not exceed 13 weeks.

Assessments of AEs and concomitant medication will be performed throughout the trial.

### Visit 1 (Screening, Day -63 to Day -29)

At the screening visit each subject will be informed about the trial and after signing the Informed Consent Form, assessments for eligibility will commence. The eligibility evaluation includes adherence to inclusion and exclusion criteria, collection of demographic data and medical history, physical examination, gynaecological examination with PAP smear (unless done within 6 months prior to screening) and transvaginal ultrasound, urine drug screen and alcohol breath test, assessment of vital signs, 12-lead ECG, blood sampling for clinical chemistry, haematology, serology, and pregnancy test, and urine sampling for urinalysis.

### Visit 2 (Run-in Period, Day -28)

All subjects found eligible at the screening will be asked to return for the run-in period Visit 2. On Day  $-28 \pm 1$ , the subject will do a urinary pregnancy test, and if negative, receive an administration of DECAPEPTYL Depot 3.75 mg. In women not receiving hormonal contraceptives the first DECAPEPTYL Depot administration should take place in the time interval 7 days before to 3 days after the expected start of menstruation. In women discontinuing combined oral contraceptives, the first DECAPEPTYL Depot administration should take place after the subjects have discontinued the hormonal contraception and within 5 days of commencement of bleeding.

### Visit 3 (Run-in Period, Day -10)

A urinary pregnancy test will be repeated on Day  $-10 \pm 1$ , and if negative, the subject will receive a second administration of DECAPEPTYL Depot 3.75 mg.

### Visit 4 (Run-in Period, Day -3)

On Day -3 a blood sample will be collected for analysis and eligibility check of the FSH concentration. The Day -3 assessment may be repeated up to 5 days later if the first FSH measurement is  $>5$  IU/L (subsequent visits will be postponed accordingly). A gynaecological examination and transvaginal ultrasound may be performed.

### Visit 5 (Run-in Period and Treatment, Day -1 to Day 3)

All subjects still found eligible after the FSH analysis will be asked to return for a treatment visit (residential stay). At the arrival to the clinic on the day before the administration day (Day -1 in the run-in period), blood sampling for analysis and eligibility check of the FSH concentration, clinical chemistry, haematology, and pregnancy test, and urine sampling for urinalysis will be performed. A limited general eligibility check (inclusion/exclusion criteria), urine drug screen, alcohol breath test, vital signs, and 12-lead ECG will also be performed. A gynaecological examination and transvaginal ultrasound will be performed if not done on Days -3 or -2.

The next day (Day 1), a blood sample for assessment of the presence of anti-FSH antibodies will be collected prior to administration of FE 999049. The subject will then be randomised to and receive an abdominal subcutaneous injection of either 12, 18, or 24 µg FE 999049. Safety assessments will be performed, injection site reactions assessed, and blood samples for PK analysis collected at predetermined time-points (Table 1). On Day 3, subsequent to the 48-hour PK sampling, the blood sampling for assessment of clinical chemistry, haematology, urine sampling for urinalysis, and assessment of vital signs and ECG, the subjects will be discharged from the clinic.

### **Visits 6 - 12 (Assessment, Day 4 to Day 10)**

The subjects will visit the clinic each day in the morning or, if agreed between investigator and subject, have a residential stay from Day 4 to Day 10 for assessment of serum concentration of FE 999049. Additionally, at Visit 9 (Day 7) a blood sample for assessment of the presence of anti-FSH antibodies will be collected.

### **Visit 13 (Follow-up, Day 11)**

A follow-up visit will be scheduled on Day 11, the day after the last assessment day. Blood samples for analysis of clinical chemistry and haematology and for a pregnancy test will be collected as well as urine samples for urinalysis. Physical examination, 12-lead ECG and vital signs will be assessed. A gynaecological examination with PAP smear and transvaginal ultrasound will also be performed. Depending on the results of the follow-up assessments, additional visits may be requested at the discretion of the investigator. Subjects should be advised to continue to use a double barrier method of contraception until menses resumes or until another contraceptive method has been established.

### **Visit 14 (Anti-FSH Antibody Assessment, Day 28)**

A visit for the collection of a blood sample for assessment of the presence of anti-FSH antibodies will be scheduled on Day 28.

The end of trial is defined as the last visit by the last subject. After this visit the subjects will be contacted once a month until return of normal menstruation.

Subjects with a treatment-induced anti-FSH antibody response on Day 28 (both with and without neutralising capacity) will be asked to return after 1, 2, 3, 6, 9, and 12 months until two consecutive assessments indicate that the anti-FSH antibody level has become negative or has returned to the baseline level.

**Table 1 Trial flow chart**

Visit No. Day	Screening	Run-in period				Treatment and Assessments								Follow-up	Anti-FSH ab		
		Ambulatory visits				Residential stay				Ambulatory visits							
	1	2	3	4	5	6	7	8	9	10	11	12	13	14			
-63 to -29	-28	-10	-3	-1	1	2	3	4	5	6	7	8	9	10	11	28	
Inclusion/exclusion criteria	X				X												
Informed Consent	X																
Randomisation					X												
Demographics	X																
Physical examination	X															X	
Medical history	X																
Gynaecological exam. and transvaginal ultrasound	X			X a	X a											X	
Cytology	X b															X	
Serum pregnancy test	X				X											X	
Urine pregnancy test		X c	X c														
FSH for eligibility determination (local laboratory)				X	X												
Blood sampling for PK determination						X d	X d	X d	X	X	X	X	X	X			
Urine drugs screen	X				X												
Alcohol breath test	X				X												
Serology	X																
Vital signs e	X			X	X f	X f	X f									X	
12-lead ECG	X			X	X f	X f	X f									X	
Clinical chemistry, haematology, and urinalysis	X			X				X								X	
Injection site reactions					X g												
Blood sampling for anti-FSH antibody analysis					X h						X					X	
Adverse events	X	X	X	X	X	X	X	X	X	X	X	X	X	X	X	X	
Prior/concomitant medication	X	X	X	X	X	X	X	X	X	X	X	X	X	X	X	X	
Administration of DECAPEPTYL Depot 3.75 mg		X	X														
Administration of IMP					X												

ab: antibody; ECG: electrocardiogram; FSH: follicle-stimulating hormone; IMP: investigational medicinal product; PK: pharmacokinetic;

a) Between Day -3 and Day -1

b) Cytology will be performed at screening if not done within 6 months prior to screening

c) Before the Day -28±1 and Day -10±1 DECAPEPTYL Depot administration

d) -1, -0.5, 0, 4, 8, 12, 16, 20, 24, 28, 32, 36, 40, 48 hours post-dose

e) Vital signs include systemic blood pressures, heart rate and body temperature

f) 12, 24 and 48 hours post-dose

g) Immediately, and 30 min and 24 hours after administration

h) Before administration of FE 999049

## 7 TRIAL ASSESSMENTS

A laboratory manual will cover all blood and urine tests and describe sampling and shipment procedures including contact details, storage conditions, equipment, volume, analytical method, reference range, etc. The manual will be provided to the clinical investigational unit before the start of the trial. The total blood volume collected for clinical laboratory assessments and PK measurements will be less than 200 ml. If deemed necessary for safety reasons extra samples may be collected.

### 7.1 Assessments Related to Endpoints

#### 7.1.1 Pharmacokinetics

Blood samples for measurement of serum concentration of FSH will be collected 1 and 0.5 hours prior to IMP administration, immediately before administration, and at 4, 8, 12, 16, 20, 24, 28, 32, 36, 40, and 48 hours, and 3, 4, 5, 6, 7, 8, and 9 days after administration. The actual sampling time at the ambulatory visits will be recorded. The serum concentrations of FSH will be analysed under the responsibility of the Department of Bioanalysis at Ferring Pharmaceuticals.

#### 7.1.2 Safety Assessments

##### 7.1.2.1 Adverse Events

See Section 8.

##### 7.1.2.2 Vital Signs

Vital signs comprising systolic and diastolic blood pressure, heart rate, and body temperature will be assessed at screening, on Day -1, and 12, 24, and 48 hours after administration of FE 999049, and at the follow-up visit. Systolic and diastolic blood pressure will be measured after the subject has been in supine position for at least 5 minutes. All recordings will be performed using validated standard equipment. Clinically significant abnormal findings will be reported as AEs.

##### 7.1.2.3 Electrocardiography

The 12-lead ECGs will be recorded at screening, Day -1, and 12, 24, and 48 hours after administration of FE 999049, and at the follow-up visit after the subjects have rested for at least 5 min in supine position. The ECG will be recorded with a validated ECG device.

ECG recordings will capture at least four QRS complexes, i.e. 3 evaluable RR intervals. The investigator or a designate will evaluate whether the ECG is normal or abnormal and whether it is clinically significant, if abnormal. Any occurrence of de- or re-polarisation disorders, arrhythmic disorders or other abnormalities will be assessed and any changes compared to the pre-medication record will be commented. ECGs may be repeated for quality reasons and the repeat used for analysis. Clinically significant abnormal findings will be reported as AEs.

#### 7.1.2.4 Laboratory Parameters

##### Clinical chemistry, haematology, and urinalysis

Blood and urine samples will be collected at screening, on Day -1, Day 3, and at the follow-up visit for safety laboratory evaluations of clinical chemistry, haematology, and urinalysis parameters according to [Table 2](#). The clinical chemistry and haematology analyses will be performed at a local laboratory.

Urinalysis will be performed locally from a sample of mid-stream urine by means of a dip-stick test. In case any result of the dipstick is abnormal, a new urine test will be performed. If the abnormal result is confirmed, further examination may be initiated at the discretion of the investigator. Clinically significant abnormal findings will be reported as AEs.

**Table 2 Safety laboratory parameters**

Clinical Chemistry	Haematology	Urinalysis
Alanine aminotransferase	Haematocrit	Protein
Albumin	Haemoglobin	Glucose
Alkaline phosphatase	Mean cellular volume (MCV)	Bilirubin
Aspartate aminotransferase	Mean corpuscular haemoglobin (MCH)	pH
Glucose	Mean corpuscular haemoglobin concentration (MCHC)	Nitrite
Calcium	Platelet count	Ketone
Chloride	Red blood cell count	Urobilinogen
Cholesterol	Reticulocytes	Blood
Creatinine	White blood cell count with differential count	Leukocytes
C-reactive protein	Neutrophils, eosinophils, basophils, lymphocytes	Specific gravity
Gamma-glutamyltransferase	Monocytes, large unclassified cells	
Phosphate		
Potassium		
Sodium		
Total bilirubin		
Triglycerides		
Urea (blood urea nitrogen)		

#### 7.1.3 Other Assessments related to Endpoints

##### 7.1.3.1 Injection Site Reactions

Injection site reactions will be assessed by the investigator immediately after injection, 30 minutes, and 24 hours after administration of the IMP. The injection site reactions to be assessed are redness, pain, itching, swelling, and bruising, each to be assessed as none, mild, moderate, or severe. These injection site reactions will not be recorded as AEs.

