## 1.3 Benefit / Risk Aspects

This is a phase 1 trial in healthy subjects and does not entail any medical benefit for the trial participants.

FE 999049 is a recombinant human FSH, and it is expected that the pharmacological effects and side effects of FE 999049 resemble those reported for other FSH products. The most frequently reported AEs in a previous single dose trial with FE 999049 in Caucasian women at doses ranging from 37.5 IU to 450 IU were headache and injection site reactions, the latter of short duration and possibly related to the volume administered. In another previous single dose trial with FE 999049 in Japanese and Caucasian women at doses ranging from 75 IU to 450 IU, the most frequently reported AEs were lower abdominal pain, vaginal haemorrhage and injection site reactions. In both trials a limited number of other AEs were sporadically reported in all treatment groups, including the placebo groups, and FE 999049 was regarded well tolerated. In the third previous single dose trial with FE 999049 in Caucasian women receiving 450 IU, the most frequently reported AEs were headache, breast tenderness and pelvic discomfort. Common side effects reported for other FSH products are ovarian enlargement, breast complaints, abdominal pain, pelvic pain, headache, gastrointestinal symptoms, injection site reactions (swelling, pain, redness), hypersensitivity reactions, and ovarian cysts. Cases of ovarian hyperstimulation syndrome (OHSS), characterised by large ovarian cysts, abdominal pain, abdominal distension, vascular leakage, and rarely associated with thromboembolic events, have occurred in multiple dose trials with other FSH products, but no signs of OHSS were observed in the previous phase 1 trials.

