## 8 ADVERSE EVENTS

### 8.1 Adverse Events

#### 8.1.1 Definitions

An adverse event is any untoward medical occurrence in a subject participating in a clinical trial. It includes:

- Any unfavourable and unintended sign, symptom or disease temporally associated with the use of the IMP, whether or not considered to be caused by the IMP.
- Adverse events commonly observed and adverse events anticipated based on the pharmacological effect of the IMP.
- Any laboratory abnormality, vital sign or finding from physical or gynaecological examination assessed as clinically significant by the investigator [note: pre-existing conditions diagnosed through assessments and examinations at the screening visit or during the screening period are not adverse events, but are recorded as medical history].
- Accidental injuries, reasons for any change in medication (drug and/or dose), reasons for any medical, nursing or pharmacy consultation, or reasons for admission to hospital or surgical procedures.
- Overdoses and medication errors with and without clinical consequences.

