### 8.2.2 Recording of Adverse Events

The investigator must record all adverse events in the Adverse Event Log provided in each subject's -eCRF with information about:

- Adverse event
- Date and time of onset (time can be omitted, if applicable)
- Intensity
- Causal relationship to the IMP
- Action taken to IMP
- Other action taken
- Date and time of outcome (time can be omitted, if applicable)
- Outcome
- Seriousness

Each of the items on the Adverse Event Log are described in detail in the following sections.

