10.4.1 Overview of Treatment Emergent Adverse Events

The summary table for treatment emergent adverse events will include the number of subjects reporting an AE, the percentage of subjects (%) with an AE and the number of events reported, for each treatment and in total, for the following categories:

- All TEAEs
- Deaths
- Serious TEAEs
- Non-serious TEAEs
- Severe TEAEs
- Moderate TEAEs
- Mild TEAEs
- Adverse drug reactions (ADRs, i.e. TEAEs with reasonable possible causal relationship to IMP)
- AEs leading to withdrawal
- Other significant AEs

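### Protocol 7.1.3.1 keeps graded injection site reactions out of the adverse event log without exception, contradicting the protocol's own rules on AE recording and SAE forms

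*Protocol*

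**What the plan says.** Protocol 7.1.3.1 sets up a solicited assessment of local tolerability. On timing it says: "Injection site reactions will be assessed by the investigator immediately after injection, 30 minutes, and 24 hours after administration of the IMP". On content: "The injection site reactions to be assessed are redness, pain, itching, swelling, and bruising, each to be assessed as none, mild, moderate, or severe". It then closes with: "These injection site reactions will not be recorded as AEs".

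The general safety rules point the other way. Protocol 8.1.1 counts as an AE "Any unfavourable and unintended sign, symptom or disease temporally associated with the use of the IMP, whether or not considered to be caused by the" [product]. The same list also names "Adverse events commonly observed and adverse events anticipated based on the pharmacological effect of the IMP". Protocol 8.2.2 then states: "The investigator must record all adverse events in the Adverse Event Log". Protocol 8.5.2 requires every SAE to be reported and makes completion of the AE Log a mandatory part of the initial report.

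For reporting, injection site reactions are an endpoint of their own (Protocol 2.2, SAP 2.2). Protocol 9.7.3.5 and SAP 10.5 tabulate them by dose group, sign, grade and time. The AE tables draw on recorded AEs only, and the SAP's overview row for drug reactions is defined as "Adverse drug reactions (ADRs, i.e. TEAEs with reasonable possible causal relationship to IMP".

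Protocol 1.3 reports that in the earlier single-dose trial in Japanese and Caucasian women "the most frequently reported AEs were lower abdominal pain, vaginal haemorrhage and injection site reactions". It also puts these reactions among the most frequent AEs in one other single-dose trial, but not in the third.

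**The concern.** Grading solicited local reactions separately is ordinary practice. The difficulty is that the exclusion carries no condition. It covers a reaction graded severe, one that needs medication, one still present after the last scheduled look, and one that meets a seriousness criterion. Elsewhere in the same chapter (Protocol 7.1.2.2 to 7.1.2.4, on vital signs, ECG and laboratory parameters) clinically significant findings are sent to AE reporting. Only 7.1.3.1 does the reverse.

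Two things are at stake. The first is data capture: an investigator who follows 7.1.3.1 records a grade and nothing else for the local reactions that matter most. The second is reporting: safety and tolerability is one of the trial's two objectives, and the overview of TEAEs and ADRs will leave out an expected local reaction to a subcutaneous product without any note that it has done so.

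**Working it through.** The point rests on text. The plan states no injection site reaction rate and no formal sample size calculation, so there is no figure of its own to reproduce beyond 3 groups x 8 subjects = 24.

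**1. Scope of the exclusion.** The sentence in 7.1.3.1 refers back to the five listed signs, which are graded up to severe. Neither document adds an exception for severity, treatment, persistence or seriousness.

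**2. Against the general AE rules.** A red, swollen or painful injection site after dosing is an unfavourable sign or symptom linked in time to the product, so it meets the first clause of the 8.1.1 definition. Section 8.2.2 then requires it to be logged, and 7.1.3.1 forbids that. The clause on anticipated events is weaker support: it speaks of pharmacological effect, whereas Protocol 1.3 suggests that the local reactions may relate to injected volume. The conflict stands on the first clause alone.

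**3. Against the SAE process.** For a serious listed reaction, 8.5.2 requires a report that includes the AE Log, while 7.1.3.1 says the event is not recorded as an AE. The site receives two incompatible instructions.

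**4. Against the medication rules.** Protocol 4.3.1 allows medication during the trial to treat AEs, apart from a few named products. Read with 7.1.3.1, other medication given for a listed reaction has no AE to attach to. Read with 8.1.1, which counts the reason for a medication change as an AE, the same reaction should be logged. The sections need to be reconciled.

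**5. What is captured instead.**

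| Item | AE route | 7.1.3.1 |
|---|---|---|
| Intensity | Yes (8.2.2) | Yes, as a grade |
| Onset and end | Yes (8.2.2) | Only present or absent at three times |
| Causality, action taken, outcome, seriousness | Yes (8.2.2) | Not specified |
| Follow-up to resolution or stability | Yes (8.6.1) | Not specified |

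Subjects are seen daily from Day 4 to Day 10, but the trial flow chart has no injection site assessment after 24 hours.

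**6. Effect on the tables.** ADRs are a subset of TEAEs, and TEAEs are a subset of recorded AEs. A listed reaction that is never recorded as an AE therefore cannot appear in SAP 10.4.1 or 10.4.2. Each subject whose only drug-related event is a listed reaction lowers the ADR proportion by 1/8 = 12.5 percentage points in her dose group and by 1/24 = 4.2 points overall.

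**7. How likely the gap is to matter.** No rate is given, so this is illustration only. If a severe or treated listed reaction occurs in a fraction p of subjects (assumed), the chance of at least one among n subjects is 1 − (1 − p)^n.

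| Assumed p | n = 8 | n = 24 |
|---|---|---|
| 1% | 8% | 21% |
| 2% | 15% | 38% |
| 5% | 34% | 71% |
| 10% | 57% | 92% |

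**The case against.** The strongest reply is that 7.1.3.1 is a specific rule displacing a general one, and that nothing important is lost. Injection site reactions are a named endpoint, actively solicited and graded by the investigator. They are displayed by dose group, sign, grade and time, including a count at any time point, and SAP 10.5 adds a category for any of the symptoms. A reader of the report will see how many subjects had a severe reaction in each group. The trial is descriptive, and no test or decision depends on the ADR proportion. All of this is right, and it rules out any claim that severe reactions disappear from the report.

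A reader might infer that serious reactions escape SAE reporting. The documents do not support that: 7.1.3.1 does not mention seriousness, and 8.5.1 and 8.5.2 define SAEs and require them to be reported with no exemption for injection site reactions. The text is contradictory; it is not a waiver.

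A reader might also infer that a reaction first appearing after 24 hours can never be an AE. That goes too far. The excluded reactions are arguably only those seen at the scheduled assessments. AEs are asked about at every visit through Day 28, and local signs outside the five remain ordinary AEs. The weakness is that the protocol leaves this to interpretation.

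Finally, it is tempting to say that the AE tables will not be comparable with those of the earlier trials. The documents do not describe how those trials collected local reactions and plan no such comparison, so this should not be pressed.

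What the reply does not answer is the direct conflict with 8.1.1, 8.2.2 and the AE Log requirement in 8.5.2, or the absence of duration, causality, outcome and follow-up for a reaction that is severe, treated or persistent.

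**Conclusion.** The point holds in a limited form. Section 7.1.3.1 contradicts the protocol's AE definition, its recording duty and its SAE form requirement. As written, it leaves a listed reaction that is serious, severe, treated or lasting beyond 24 hours without a consistent route into the AE log. For such a reaction the plan secures at most a grade at three times. Listed reactions of every grade are absent from the TEAE and ADR tables, at 12.5 points per affected subject in a dose group of 8, while remaining visible in the separate injection site table.

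That per-subject figure assumes that the subject has no other event already counted in the ADR row and that the reaction would have been judged drug-related. How many subjects are affected cannot be derived from the documents. The consequence is incomplete and ambiguous safety capture. It does not affect the pharmacokinetic results. It is worth correcting mainly because the correction is so cheap.

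**What to change.** Keep the solicited grading and the separate table. Amend Protocol 7.1.3.1 to say that a listed reaction that is serious, is graded severe, is treated, or starts or persists after the 24-hour assessment is also entered in the AE log with the usual investigator causality judgement, and that SAE reporting is unaffected. This reconciles 7.1.3.1 with 8.1.1, 8.2.2 and 8.5.2 for the reactions that matter.

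Add a footnote to the TEAE and ADR tables in SAP 10.4.1 and 10.4.2 stating that all other listed injection site reactions are reported separately under SAP 10.5. Do not add every graded reaction to an ADR count. Protocol 9.7.3.4.1 defines ADRs by the investigator's causality judgement, which the grading in 7.1.3.1 does not include, and there is no placebo group to separate needle or volume effects.

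The cost is a short protocol amendment and a table footnote. The small downside is that a few events will appear in two displays, which the footnote should mention.
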